### **Data Collection**

The following data will be collected at the time of randomization:

Recipient demographics- such as age at transplantation, sex and race.

Clinical history- Causes of end-stage renal disease, past medical history

Transplant related information- donor age, cadaveric versus living kidney transplant, histocompatibility and cross match data, viral serology, history of acute rejection and delayed graft function, use of induction therapy and immunosuppressants, use of ACEI and/or ARB, level of renal allograft function- estimated GFR (e-GFR(12) using MDRD formula, proteinuria.

Peripheral blood leukocytes will be obtained from renal transplant recipients for baseline (prior to randomization) lymphocytes functional activity and characterization of lymphocytes subpopulations by flow cytometry analysis.

Peripheral donor leukocytes (from living donor patients) will also be obtained at the time of randomization. These donor leukocytes will be used as stimulator cells to study the functional activity of the recipient's lymphocytes function.

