### **Research Objective**

The aim of the present study is to prospectively investigate the impact of CI conversion (tacrolimus→sirolimus) between 6 and 24 months post-transplant on the incidence of acute cellular rejection, renal allograft function and lymphocytes function.

Primary aim of the study is:

to investigate the impact of CI conversion (tacrolimus→sirolimus) on the incidence of acute cellular rejection.

Secondary aims of the study are:

- i) evaluate whether CI conversion (tacrolimus→sirolimus) contributes positively or negatively on the renal allograft function calculated with e-GFR and proteinuria;
- ii) patient and graft survival ;
- iii) evaluate if CI conversion impacts on lipid profile, incidence of hypertension, malignancies, and opportunistic infections and post-transplant DM;
- iv) evaluate possible modifications of lymphocytes function before and after conversion (tacrolimus→sirolimus)
- v) assess tubular toxicity by evaluating urinary biomarkers

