### **Post randomization**

The recipients assigned to continue with tacrolimus and MMF will be routinely followed at our outpatient Transplant center with monthly labs. In addition to the baseline pre-randomization labs, at 6, 12 and 24 months post randomization, peripheral blood leukocytes will be obtained to study lymphocytes functional activity and to characterize lymphocytes subpopulations by flow cytometry analysis.

Post randomization, the recipients assigned to switch from tacrolimus to sirolimus and continue with MMF will be routinely followed at our Transplant center with monthly labs. Furthermore, during the period of conversion from tacrolimus to sirolimus, weekly labs will be obtained to monitor renal function and bone marrow function. In addition to the baseline pre-randomization labs, and labs collected at 6, 12, 24, 36, and 48 months post randomization, peripheral blood leukocytes will be obtained to study lymphocytes functional activity to characterize lymphocytes subpopulations by flow cytometry analysis and urine will be collected to assess tubular toxicity by evaluating urinary biomarkers.

Both groups of patients will be followed for 4 years post-randomization. In addition to monitoring renal allograft function, we will evaluate the incidence of acute rejection, patient and graft survival, the impact of CI conversion on the lipid profile, the incidence of hypertension, malignancies, opportunistic infections and post-transplant DM.

Furthermore, with the peripheral leukocytes obtained at baseline prior to randomization and at 6, 12, 24, 36, and 48 months post-randomization we will investigate possible modifications of lymphocytes function and of the lymphocytes subpopulations that might have occurred as a consequence of the switch from tacrolimus to sirolimus.

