### **Exclusion Criteria**

- 1) Subjects with ESRD secondary to primary FSGS (focal segmental glomerulonephritis).
- 2) Inability to comply with study procedures
- 3) Inability to sign the informed consent
- 4) Subjects with a significant or active infection
- 5) Subjects who are pregnant or nursing females
- 6) Subjects with a history of severe hyperlipidemia not controlled with statins, patients with at total cholesterol of  $> 400$  mg/dl
- 7) Subjects with a platelet count  $< 100,000\text{mm}^3$  WBC  $< 2,000\text{mm}^3$
- 8) Subjects with severe proteinuria at the time of randomization ( $> 2\text{gm/day}$ )
- 9) Subjects with more than 2 episodes of acute cellular rejection post transplantation will be excluded from this study
- 10) An estimated GFR  $< 40$  cc/min (This will be calculated by MDRD or by Cockcroft-Gault formulas, which are both are commonly used formulas for estimated GFR.)
- 11) A history of malignancy during the post-transplant period (other than treated basal cell cancer and/or squamous cell cancer)
- 12) Subjects, who, due to the existence of a surgical, medical or psychiatric condition, other than the current transplant, which in the opinion of the investigator, precludes enrollment into this trial
- 13) A history of ACR during the most recent previous 3 months prior to randomization

\*\*Other: prior to approaching any individual who has undergone desensitization procedures prior to transplant, we must first check with Dr. [name]

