### **Stopping Rules**

Subjects diagnosed with two acute renal allograft rejection episodes post conversion from tacrolimus to sirolimus will be stopped from participating in the study and will be switched back to tacrolimus.

Subjects that develop significant side effects secondary to sirolimus (severe thrombocytopenia (platelets count <50, 000); severe hyperlipidemia not controlled by the use of statins or other cholesterol lowering agents; worsening proteinuria or severe de-novo proteinuria) will have sirolimus stopped and patients will be switched back to tacrolimus.

Subjects developing post-transplant infections (i.e., UTI, CMV, HSV, EBV, HCV, HBV, HIV, PCP), that in the opinion of the investigator are detrimental to the subject and their participation in this research trial, will be stopped from participating in this study.

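### The lipid comparison plans no use of a baseline cholesterol that eligibility already requires, and so gives up precision

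*Combined protocol and SAP*

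**What the plan says.** **Outcome.** Secondary aim iii in Research Objective is to "evaluate if CI conversion impacts on lipid profile, incidence of hypertension, malignancies, and opportunistic infections and post-transplant DM". Post randomization repeats lipid profile among the outcomes evaluated in both groups over 4 years. Neither section names an analyte or a visit.

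**Baseline.** The clinical items in Data Collection finish with "level of renal allograft function- estimated GFR (e-GFR(12) using MDRD formula, proteinuria". Use of ACE inhibitors or ARBs is listed; lipids and statin use are not.

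**Eligibility.** Exclusion criterion 6 reads "Subjects with a history of severe hyperlipidemia not controlled with statins, patients with at total cholesterol of" more than 400 mg/dl. No date window is given for the value.

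**Follow-up bloods.** In the tacrolimus arm, "The recipients assigned to continue with tacrolimus and MMF will be routinely followed at our outpatient Transplant center with monthly labs". The sirolimus arm likewise "will be routinely followed at our Transplant center with monthly labs". Baseline laboratory tests before randomisation are also mentioned. The content of these panels is not stated. During conversion, in the sirolimus arm only, "weekly labs will be obtained to monitor renal function and bone marrow function".

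**Stopping.** Stopping Rules lists, as a reason to stop sirolimus, "severe hyperlipidemia not controlled by the use of statins or other cholesterol lowering agents". No matching rule is written for the tacrolimus arm.

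**Analysis.** Statistical Analysis gives two-sample t tests for continuous variables and chi-square tests for discrete ones. The only multivariable model is a logistic regression for acute rejection and renal allograft function.

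**The concern.** Eligibility needs a total cholesterol from every subject, and lipid profile is an outcome, but the plan does not carry the one into the analysis of the other. Renal function, the outcome of aim i, has its baseline listed; the lipid outcome does not. The analysis section mentions no baseline covariate. Cholesterol differs between people and is likely to be correlated within a person over time. A t test on follow-up values leaves all the between-person variation in the error term, when part of it could be removed with a number that must already exist.

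What is at stake is the sharpness of one secondary comparison. The plan itself treats lipids as a concern, since they appear in an aim, an exclusion criterion and a stopping rule.

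A second, smaller matter is timing. Because the plan does not say which scheduled panels include lipids, it does not assure that both arms contribute values from the same visits.

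**Working it through.** The plan states no sample size, power, SD or effect size for lipids, so there is no figure to reproduce. The calculation below only illustrates the size of the loss.

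**Inputs from the documents**
- 275 subjects randomised 2:1 (Randomization): 275 × 2/3 ≈ 183 and 275 × 1/3 ≈ 92.

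**Inputs assumed**
- Two-sided 5% and 80% power: 1.960 + 0.842 = 2.802.
- Full retention, and one follow-up value per subject at a given visit.
- Correlation r between baseline and follow-up cholesterol: 0.3, 0.5 or 0.7.

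**Formulas, in SD units**
- Follow-up value only: d = 2.802 × √(1/92 + 1/183) = 2.802 × 0.1278 = 0.358.
- Adjusted for baseline: d × √(1 − r²).

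| r | Residual variance, 1 − r² | Reduction | Detectable difference | Power at 0.358 SD | Follow-up-only N for equal precision, 275/(1 − r²) |
|---|---|---|---|---|---|
| not adjusted | 1.00 | – | 0.358 SD | 80% | 275 |
| 0.3 | 0.91 | 9% | 0.342 SD | 83.6% | 302 |
| 0.5 | 0.75 | 25% | 0.310 SD | 89.9% | 367 |
| 0.7 | 0.51 | 49% | 0.256 SD | 97.5% | 539 |

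**If the t test were meant for change from baseline.** The section does not say. With equal SDs at both times, change has variance factor 2(1 − r): 1.4, 1.0 and 0.6 at r = 0.3, 0.5 and 0.7. The adjusted model gives 0.91, 0.75 and 0.51, so it is more precise than either t test at each of these correlations.

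**If fewer subjects are enrolled.** The Biopsy section puts 46 + 93 = 139 subjects at 70% of enrolment, which implies 139/0.7 ≈ 199 rather than 275. With about 66 v 133, the unadjusted figure is 2.802 × √(1/66 + 1/133) ≈ 0.42 SD. Adjustment at r = 0.5 to 0.7 gives about 0.37 to 0.30 SD. The proportional gain is the same. The formula is symmetric, so it does not matter which arm is larger.

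**The case against.** The strongest reply has four parts.

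1. **Absence from a list is not absence from the record.** The case report form is not among the documents, and an entry cholesterol should be in the source notes. This stands: the value could be retrieved. It does not answer the analysis section, which gives a baseline no role.

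2. **The gain is the generic one from baseline adjustment, and the correlation is assumed.** This also stands. Over 4 years, with statins in use, r may be low, and at 0.3 the gain is only 9% of the variance. Withdrawals would reduce the numbers further, since only survival data are firmly sought after withdrawal. No stated figure in the plan is contradicted.

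3. **The t test on follow-up values alone is inferred.** True, since the section does not say whether the variable is a follow-up value or a change. The working shows that adjustment is preferable in both cases.

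4. **Nothing shows that the arms are measured differently.** A reader might infer that lipids are drawn at the clinicians' discretion, more often on sirolimus because only that arm has a lipid stopping rule, and that the comparison is therefore biased. The documents do not support this. Both arms have scheduled monthly bloods, which may or may not include lipids. The wording about renal and bone marrow function describes only the weekly tests during conversion, so it neither defines the routine panels nor shows extra lipid testing. The stopping rule supplies a possible motive for unequal testing and no evidence of it. With a common schedule, randomisation keeps even a follow-up-only comparison free of bias.

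**Conclusion.** The point holds as a loss of precision on one secondary outcome. The plan needs a cholesterol at entry, does not list it among the randomisation data, and analyses continuous outcomes without adjustment. Under the assumptions above (92 v 183, two-sided 5%, 80% power, full retention), adjustment lowers the detectable difference from 0.358 SD to 0.342, 0.310 or 0.256 SD at r = 0.3, 0.5 or 0.7. The correlation is not in the documents, so the whole range should be kept in view, including the weak case.

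Common timing of lipid values is not assured, because panel content is unstated. Unequal testing between arms is a possible risk to guard against, not a documented fact, and no bias should be claimed from it. This is a worthwhile minor improvement and does not threaten the trial's main conclusions.

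**What to change.** - **Data Collection:** add the total cholesterol used for exclusion criterion 6, with its date, and statin use, as baseline in both arms. The criterion names total cholesterol only, so a full lipid panel at entry cannot be presumed.
- **Post randomization:** state that total cholesterol is measured on the scheduled blood draws at 6, 12, 24, 36 and 48 months in both arms. The tacrolimus paragraph lists leukocyte sampling only to 24 months, but the monthly bloods can supply the later visits.
- **Statistical Analysis:** compare follow-up total cholesterol by a linear model with arm and baseline cholesterol, in place of the t test. Name in advance which visit is the main one. Use only the common scheduled values for the arm comparison; values drawn at other times serve care and safety reporting.

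None of this touches treatment or the stopping rules. The cost is a case report form entry at baseline and, if lipids are not already in the routine panel, a small laboratory charge on blood that is being drawn anyway. If they are already in the panel, the sponsor need only say so.

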### **Post randomization**

The recipients assigned to continue with tacrolimus and MMF will be routinely followed at our outpatient Transplant center with monthly labs. In addition to the baseline pre-randomization labs, at 6, 12 and 24 months post randomization, peripheral blood leukocytes will be obtained to study lymphocytes functional activity and to characterize lymphocytes subpopulations by flow cytometry analysis.

Post randomization, the recipients assigned to switch from tacrolimus to sirolimus and continue with MMF will be routinely followed at our Transplant center with monthly labs. Furthermore, during the period of conversion from tacrolimus to sirolimus, weekly labs will be obtained to monitor renal function and bone marrow function. In addition to the baseline pre-randomization labs, and labs collected at 6, 12, 24, 36, and 48 months post randomization, peripheral blood leukocytes will be obtained to study lymphocytes functional activity to characterize lymphocytes subpopulations by flow cytometry analysis and urine will be collected to assess tubular toxicity by evaluating urinary biomarkers.

Both groups of patients will be followed for 4 years post-randomization. In addition to monitoring renal allograft function, we will evaluate the incidence of acute rejection, patient and graft survival, the impact of CI conversion on the lipid profile, the incidence of hypertension, malignancies, opportunistic infections and post-transplant DM.

Furthermore, with the peripheral leukocytes obtained at baseline prior to randomization and at 6, 12, 24, 36, and 48 months post-randomization we will investigate possible modifications of lymphocytes function and of the lymphocytes subpopulations that might have occurred as a consequence of the switch from tacrolimus to sirolimus.

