### **Randomization**

For this research study, between 6 and 24 months post-transplant we plan to prospectively randomize 2:1 renal transplant patients to either:

- Continue with tacrolimus and MMF or
- Substitute tacrolimus with sirolimus and continue MMF

A total of 400 pts. are expected to be screened for the randomization and we expect to be able to randomize 275 renal transplant patients into this protocol.

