## **Primary Safety Endpoints**

The primary safety endpoints will be assessed on the adverse events (AEs) and serious adverse events (SAEs) that are observed throughout the trial.

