### **Abnormal Laboratory Values**

A clinical laboratory abnormality should be documented as an adverse event if any one of the following conditions is met:

- The laboratory abnormality is not otherwise refuted by a repeat test to confirm the abnormality
- The abnormality suggests a disease and/or organ toxicity
- The abnormality is of a degree that requires active management; e.g. change of dose, discontinuation of the drug, more frequent follow-up assessments, further diagnostic investigation, etc.

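### During conversion the sirolimus arm has about four times as many renal and marrow lab draws as controls, and the analysis has no rule for the resulting unequal detection of laboratory adverse events

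*Combined protocol and SAP*

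**What the plan says.** Under Post randomization, the control arm's schedule reads: "The recipients assigned to continue with tacrolimus and MMF will be routinely followed at our outpatient Transplant center with monthly labs". The sirolimus arm has the same routine monthly labs, with one addition: "during the period of conversion from tacrolimus to sirolimus, weekly labs will be obtained to monitor renal function and bone marrow function". The section does not say how long conversion lasts, or whether the weekly draws replace the monthly draw or come on top of it. On duration it says "Both groups of patients will be followed for 4 years post-randomization".

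Primary Safety Endpoints states: "The primary safety endpoints will be assessed on the adverse events (AEs) and serious adverse events (SAEs) that are observed throughout the trial". Abnormal Laboratory Values sets the recording rule: "A clinical laboratory abnormality should be documented as an adverse event if any one of the following conditions is met". Three conditions follow. The first is "The laboratory abnormality is not otherwise refuted by a repeat test to confirm the abnormality". The other two are that the value suggests disease or organ toxicity, or that it needs active management, which includes closer follow-up or further investigation.

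The Study drugs sections make sirolimus and tacrolimus open label. Statistical Analysis names t tests, chi-square tests and a multivariable logistic regression. It does not mention testing frequency, scheduled versus extra draws, or a sensitivity analysis.

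**The concern.** The number of laboratory adverse events recorded depends on how often one looks as well as on how often abnormalities occur. Here the extra looking is confined to one arm, falls just after the drug switch, and covers the two systems (kidney and marrow) in which transient abnormalities are expected. One qualifying condition is enough to make a value an adverse event, and nothing in the plan brings the two arms back to a common basis.

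If the arms are compared on all recorded events, an early excess on sirolimus would mix true toxicity with added surveillance, and the reader could not separate them. The direction is known: it works against sirolimus. The weekly labs are not at fault. What is missing is an analysis that allows for them.

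**Working it through.** The plan gives no draw count or ratio, so there is no stated figure to reproduce.

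**Inputs from the documents:** monthly labs in both arms; weekly renal and marrow labs in the sirolimus arm during conversion only; 48 months of follow-up; 275 patients randomized 2:1.

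**Assumptions:** conversion length c (not stated), per-draw abnormality rates, and how long an abnormality lasts.

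**1. Draws inside the window.** Weekly against monthly is 52.18 / 12 = 4.35 to 1. If the weekly draws are added to the monthly one, it is 5.35 to 1.

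**2. Draws over follow-up.** With T months of follow-up, the ratio is (4.35c + T − c) / T if weekly draws replace monthly ones, and (4.35c + T) / T if they are added.

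| c (assumed) | T = 12, replaced | T = 48, replaced | T = 48, added |
|---|---|---|---|
| 1 month | 1.28 | 1.07 | 1.09 |
| 3 months | 1.84 | 1.21 | 1.27 |
| 6 months | 2.67 | 1.42 | 1.54 |

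For c = 3 and T = 48: (13.05 + 45) / 48 = 1.21.

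**3. From draws to detection.** An abnormality lasting d days is seen by draws every L days with probability min(1, d/L).

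| d | Weekly (L = 7) | Monthly (L = 30.4) | Ratio |
|---|---|---|---|
| 7 days | 1.00 | 0.23 | 4.3 |
| 14 days | 1.00 | 0.46 | 2.2 |
| 21 days | 1.00 | 0.69 | 1.4 to 1.5 |
| 30 days or more | 1.00 | 1.00 | 1.0 |

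The fourfold ratio therefore applies to abnormalities of a week or less. It disappears for those lasting a month.

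**4. Patients with at least one abnormal draw.** With independent draws, the chance is 1 − (1 − p)^k.

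- Inside a 1-month window (4 vs 1 draws), p = 5%: 19% vs 5%.
- Inside a 3-month window (13 vs 3 draws): 49% vs 14% at p = 5%, and 23% vs 6% at p = 2%.
- Over 48 months (51 draws for c = 1 or 58 for c = 3, vs 48 in controls): 93% to 95% vs 91% at p = 5%, and 64% to 69% vs 62% at p = 2%.

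Independence overstates the gap when abnormalities persist from one week to the next.

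**5. Event counts.** The planned biopsy numbers (93 sirolimus, 46 tacrolimus) indicate that sirolimus is the larger arm, so about 275 × 2/3 = 183 patients. With c = 3, each has about 13 − 3 = 10 extra draws, or about 1,800 in all. If 0.5% to 2% of these produced an event that would otherwise go unrecorded, that is about 9 to 37 extra records, all in one arm.

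**The case against.** A reader might infer that the sirolimus arm has four times the chance of a laboratory adverse event across the trial. The documents do not support that. Both arms share the monthly schedule for four years, the weekly draws are limited to conversion, and safety is assessed throughout the trial. On that horizon the draw ratio is close to 1 for a short conversion, and the difference in patients ever flagged falls to a few percentage points. Draws are also not events: the Adverse Event definition requires consequences, symptoms or clinical significance for an abnormal result, and a weekly repeat can itself refute an earlier value. All of this stands. It limits the problem to the conversion window and to transient findings.

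It does not remove the problem. Any one condition suffices under Abnormal Laboratory Values, so a brief abnormality that prompts closer follow-up counts even if the next draw is normal. One lasting two or three weeks would survive a weekly repeat and could still fall between two monthly draws. Event counts and early safety summaries would be affected even where the four-year proportion of patients is not.

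A second tempting inference is that closer renal monitoring inflates rejection, the primary aim. No section states a laboratory trigger for a biopsy, and the treatment section refers to biopsy-confirmed rejection. A lasting creatinine rise would appear at the next monthly lab, so weekly labs may mainly change the date of detection. The link is plausible but not documented, and the plan gives nothing from which to size it.

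Finally, closer monitoring during a drug switch is ordinary safety practice, and a table that left out its findings would hide early toxicity. That is right, and it shapes the fix.

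**Conclusion.** The point holds within limits. During a conversion period of undefined length, the sirolimus arm has about 4.35 times the renal and marrow draws of controls. Over 48 months the ratio is about 1.07 to 1.42 for assumed conversions of 1 to 6 months with weekly draws replacing monthly ones, and up to 1.54 if they are added. Abnormalities lasting under about a month and seen only on the extra draws can become adverse events in one arm only, and the analysis plan does not address this. The bias runs against sirolimus and is concentrated early. Its size in events cannot be fixed from the documents, because conversion length, per-draw rates and duration of abnormalities are all assumptions. It is a cheap improvement to the safety analysis. It does not show that the trial-wide safety comparison is distorted fourfold, or that the rejection comparison is biased.

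**What to change.** - Keep the weekly safety labs and the full table of all adverse events unchanged.
- Flag each laboratory record as common monthly or extra weekly. State in advance which draw counts as the monthly one while weekly labs are running.
- Add a between-arm comparison of laboratory adverse events restricted to the monthly draws common to both arms. Show abnormalities found only on extra weekly draws separately, beside it.
- Base any statement of excess laboratory toxicity on the full and restricted tables together.
- Do not add a rejection analysis that leaves out episodes first prompted by a weekly lab. It could remove real events from the sirolimus arm only, just after tacrolimus is stopped, and so favour sirolimus on the primary aim.

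The cost is a data flag, a few sentences in Statistical Analysis and one extra table. Patient care does not change. The drawback is that the restricted comparison may miss brief early sirolimus toxicity, which is why the full table has to stay beside it.

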### **Methods**

#### **Immediate Post Transplant Period**

Patients will receive immunosuppressive therapy as follows:

Induction immunotherapy:

- 1) Campath®/alemtuzumab (Anti CD52 humanized monoclonal antibody) (30mg IV), on the day of the kidney transplant,
- 2) methylprednisolone (500 mg IV) on the day of transplant and on day 1 (250 mg IV) and 2 (125 mg IV) post-transplant.

No further steroid will be given post-transplant unless indicated by the following medical conditions: acute renal allograft rejection, renal disease that might require the use of steroids and other systemic diseases such as rheumatoid arthritis (RA), systemic lupus erthematosus (SLE), asthma. Patients

will receive tacrolimus and Cellcept®/mycophenolate mofetil/MMF. The above medication regimen is our standard of care for renal transplant patients, and has been since 2000.

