## **Statistical Analysis**

Once the 2 groups of renal transplant patients are identified, two sample t tests will be used to compare differences in continuous variables between groups; chi square tests will be used to compare differences in discrete variables. Multivariable logistic regression analysis will be also performed to identify the combination of clinical variable that are significantly associated with the development of acute rejection and renal allograft function after conversion from tacrolimus →sirolimus.

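### The lymphocyte aim is worded as before versus after the switch; it should name a between-arm difference adjusted for the pre-randomisation value and time since transplant

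*Combined protocol and SAP*

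**What the plan says.** Secondary aim iv, under Research Objective, is to "evaluate possible modifications of lymphocytes function before and after conversion". Only patients assigned to sirolimus convert, and the aim names no comparison with the tacrolimus arm. The last paragraph of Post randomization puts the question causally, asking about changes in lymphocyte function and "lymphocytes subpopulations that might have occurred as a consequence of the switch from tacrolimus to sirolimus".

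Three features of timing and sampling bear on this:

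- **Induction.** Patients in both arms receive "Campath®/alemtuzumab (Anti CD52 humanized monoclonal antibody) (30mg IV), on the day of the kidney transplant" (Immediate Post Transplant Period).
- **Baseline.** The Randomization section says "between 6 and 24 months post-transplant we plan to prospectively randomize 2:1 renal transplant patients to either" of the two regimens. Data Collection adds: "Peripheral blood leukocytes will be obtained from renal transplant recipients for baseline (prior to randomization) lymphocytes functional activity". The baseline sample is therefore taken 6 to 24 months after induction, in both arms.
- **Follow-up.** For the tacrolimus arm, Post randomization says "at 6, 12 and 24 months post randomization, peripheral blood leukocytes will be obtained to study lymphocytes functional activity". For the sirolimus arm it lists 6, 12, 24, 36 and 48 months. The last paragraph of the section then gives the longer list without naming an arm.

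Statistical Analysis says "two sample t tests will be used to compare differences in continuous variables between groups". It does not say whether the variable is a follow-up value or a change from baseline, at which visit it is tested, or whether any covariate enters. The one multivariable model in that section is logistic and is directed at acute rejection and renal function.

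**The concern.** A change measured within the converted patients alone combines two things: the effect of replacing tacrolimus, and whatever would have happened over the same months without the switch. Every patient has had a lymphocyte-directed antibody 6 to 24 months before baseline, so counts and function may still be moving when the clock starts. If aim iv is analysed as literally worded, that movement would be read as an effect of sirolimus.

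The analysis section leaves room for this. The aim asks a before-and-after question, the named test is between groups, and nothing connects them, so two analysts could follow the text and do different things.

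A second cost falls on the between-arm test itself. The baseline sample and the time since transplant are both available, but no use of either is stated. The 18-month spread in time since induction at baseline may add between-patient variation that an unadjusted test leaves in the error term.

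**Working it through.** The documents give no sample size, power, effect size or SD for the lymphocyte outcomes, so there is no figure of the plan's own to reproduce. The check has three parts.

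**1. What a shared time trend does to each analysis**

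Inputs:
- 275 randomised 2:1 (Randomization). 275 × 2/3 ≈ 183 and 275 × 1/3 ≈ 92.
- Sirolimus is taken as the larger arm. This is inferred from the Biopsy section, which expects about 93 sirolimus and 46 tacrolimus subjects.
- Assumed: no drug effect; the same mean drift d in both arms, from 0 to 0.5 in units of the SD of the change score; two-sided alpha 0.05.

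For the within-sirolimus one-sample test, the test statistic is centred at d × √183 = 13.53 d. At d = 0.2 this is 2.71, and the chance of exceeding 1.96 is about 77%. For the between-arm test on change, the expected difference is d − d = 0 whatever d is. Simulation of 10,000 trials per row gave these false-positive rates:

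| Shared drift (SD of change) | Within sirolimus arm | Between arms, on change |
|---|---|---|
| 0 | 5.0% | 5.3% |
| 0.1 | 27% | 4.9% |
| 0.2 | 77% | 5.1% |
| 0.3 | 98% | 5.1% |
| 0.5 | 100% | 4.8% |

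A further run let drift depend on time since transplant: uniform entry over 6 to 24 months, with drift falling linearly from 0.6 SD at 6 months to 0 at 24. The rates were 97.5% within the sirolimus arm and 4.9% between arms.

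**2. What adjustment for baseline gains in the between-arm comparison**

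Assume equal variances at baseline and follow-up (set to 1) and correlation r between them. The variance per patient is 1 for a follow-up value, 2(1 − r) for a change score, and 1 − r² after baseline adjustment.

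- Reduction against a follow-up-only t test: r².
- Reduction against a change-score t test: 1 − (1 − r²) / [2(1 − r)] = (1 − r)/2.

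| Assumed r | Residual variance, 1 − r² | Cut against follow-up-only | Cut against change score |
|---|---|---|---|
| 0.3 | 0.91 | 9% | 35% |
| 0.5 | 0.75 | 25% | 25% |
| 0.7 | 0.51 | 49% | 15% |

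Adjustment gains under either reading of the planned t test. A 25% cut is worth about a third more patients (1/0.75 = 1.33). Any gain from also adjusting for months since transplant is extra, and cannot be sized from the documents.

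**3. Which visits have a concurrent control**

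| Visit | Tacrolimus arm (arm-specific text) | Sirolimus arm (arm-specific text) | Last paragraph, arm not named |
|---|---|---|---|
| Baseline | yes | yes | yes |
| 6, 12, 24 months | yes | yes | yes |
| 36, 48 months | not listed | yes | yes |

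On the arm-specific text, two of the five post-baseline visits have no control lymphocyte sample, and only a single-arm reading is possible there.

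**The case against.** A reader might infer something stronger: that recovery after alemtuzumab is confounded with the drug change by design, so that aim iv cannot be answered. The documents do not support that. Patients are randomised, the tacrolimus arm has the same assays at baseline, 6, 12 and 24 months, and the analysis section compares groups. A drift common to both arms cancels in that comparison. Time since transplant is balanced in expectation, so leaving it out costs precision and does not bias the result.

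Nor do the documents show that the planned t test ignores the baseline sample. They do not say what is tested; a two-sample test on change from baseline would use that sample and would address before and after. The fault is under-specification.

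Two further points are fair. No single-arm test is named anywhere, and the Post randomization wording is exploratory and follows a paragraph about both groups, so asking what the switch caused is compatible with a controlled comparison. The documents also say nothing about lymphocyte recovery after induction, so its presence and size in this window are assumptions.

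What remains is that aim iv, as worded, permits the single-arm reading; no between-arm estimand is stated for it; two available covariates have no stated role; and the sampling text conflicts at 36 and 48 months.

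**Conclusion.** The point holds as one of specification and precision for a secondary aim. Through month 24 the design can separate drug from time, and the plan should say that this is how aim iv will be answered.

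If the wording were followed literally within the sirolimus arm, a modest shared drift of 0.1 to 0.3 SD would give false-positive rates of 27% to 98%. These rates rest on the assumed drift and about 183 patients with paired samples. They describe a possible reading, not the named test. Any shared trend, whether or not it is recovery after induction, would have the same effect.

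For the between-arm comparison, baseline adjustment saves 9% to 49% of variance against a follow-up-only test, or 35% to 15% against a change-score test, over correlations of 0.3 to 0.7 with equal variances.

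At 36 and 48 months, time and drug would be inseparable if the control arm is not sampled; the documents are inconsistent on whether it is.

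**What to change.** 1. **Research Objective, aim iv, and the last paragraph of Post randomization.** State the question as the difference between randomised arms in lymphocyte function and subpopulations at the shared visits of 6, 12 and 24 months. Label within-arm changes from baseline as descriptive, and do not attribute them to the switch.
2. **Statistical Analysis.** For these outcomes, replace the unadjusted t test with ANCOVA at each visit, or a mixed model over the three visits with arm, visit and their interaction. Include the pre-randomisation value and months since transplant as covariates. As alemtuzumab is given on the day of transplant, the latter also measures time since induction.
3. **Post randomization.** Reconcile the arm-specific sampling lists with the last paragraph for 36 and 48 months. If the tacrolimus arm is not sampled at those visits, treat the sirolimus data there as descriptive only.

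The cost is wording in three sections. The baseline sample is already planned in both arms, and the transplant date must be known to apply the 6-to-24-month window. No new samples or visits are needed for the comparison at 6, 12 and 24 months.
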